1. PROJECT TITLE

Enhancing transdiagnostic mechanisms of cognitive dyscontrol using computer-based training

4. ESTIMATED DURATION OF THE STUDY

5 years

5. LAY LANGUAGE SUMMARY OR SYNOPSIS (no more than one paragraph)

Mood, anxiety, and traumatic stress disorders are common psychiatric conditions - affecting over 40 million U.S. adults - and are leading causes of disability worldwide. People with these conditions are commonly plagued by difficulty controlling distressing personal thoughts and memories, collectively referred to as repetitive negative thinking symptoms. Models suggest that repetitive negative thinking is driven by executive functioning deficits, such that cognitive resources are insufficient to downregulate unwanted thoughts. Executive functioning deficits could be a promising treatment target but are not typically addressed with existing interventions. The long-term goal advanced by this project is to develop effective, mechanistic cognitive training programs that can improve cognition and reduce symptoms associated with mood, anxiety, and traumatic stress disorders. The objectives of this proposal are first to determine the optimal dose of a cognitive training program designed to improve executive functioning in this population using behavioral and neural outcomes. Our central hypothesis is that repeated training exercises will enhance executive functioning and will lead to a reduction of repetitive negative thinking in mood, anxiety, and traumatic stress disorders. The project will randomize participants with depression, anxiety, and/or traumatic stress disorders to one of two doses of cognitive training or a no-treatment control condition. We will examine executive functioning change with cognitive task performance and functional neuroimaging assessments. We will assess the relationship between change in executive functioning and clinical symptoms.

6. SPECIFIC AIMS

Improving control over working memory interference is theorized to be the most effective executive functioning manipulation for targeting clinical symptoms for mood, anxiety, and traumatic stress disorders. We will test whether two doses of COGNitive Enhancement Training (COGENT; 8 vs. 16 sessions) modify control over working memory interference across multiple units of analysis as compared to a no-training control condition.

Aim 1: Identify the cognitive effects and optimal dose of COGENT to improve executive functioning measured behaviorally (cognitive task) and neurally (fMRI). We hypothesize that individuals completing COGENT will show improved executive functioning on behavioral and neural measures relative to those assigned to the waitlist condition. An effect size benchmark will be used to evaluate whether there is added

benefit to completing more training sessions (16 versus 8) over the four week period to evaluate optimal dosing.

Aim 2: Evaluate the clinical effects of the COGENT program. We hypothesize that individuals completing COGENT will show a reduction in repetitive negative thinking. We will assess whether there are additional reductions in mood and anxiety symptoms.

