9. RESEARCH DESIGN AND METHODS

The proposed study is a randomized controlled trial of COGENT versus a no-training control (repeated assessment only) in participants with clinically elevated repetitive negative thinking symptoms. We will use a parallel group design. Primary assessment will include behavioral (cognitive task performance) and imaging-based assessments (fMRI) of control over working memory interference at two time points: baseline pre-training and immediately post-training. Neural activation will be used to assess generalization of training effects across multiple units of analysis. Within the COGENT intervention arm of the study, 8 and 16 sessions will be tested to determine optimal dose. Doses were selected based on our pilot work and empirical recommendations for maximizing cognitive training effects. **Hypotheses:** We hypothesize that COGENT will 1) improve behavioral performance on a cognitive task that assesses control over working memory interference, and 2) increase neural activation within the frontoparietal network during task-based fMRI compared to the control condition. We hypothesize that COGENT will improve symptoms relative to waitlist.

All procedures are considered experimental (i.e., not standard care) and solely for research purposes.

Participants

Approximately **95** participants endorsing elevated mood, anxiety, and/or traumatic stress symptoms who endorse repetitive negative thinking will be recruited and enrolled. Previous validation studies suggest that a cutoff score of 32 on the Repetitive Thinking Questionnaire-10 adequately detects clinically severe repetitive negative thinking. We anticipate that the sociodemographic makeup of the sample will reflect the distribution of biological sex, race, and ethnicity of the San Diego community. As prevalence of internalizing disorders is higher in women than men, it is possible that women may be overrepresented in the sample.

Procedures

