COGENT, dose, and randomization: Following the baseline assessments, participants will be randomized to receive COGENT for 4 weeks (n=32) or an assessment-only control condition that receives clinical, cognitive, and MRI assessments at the same time points (n=32), stratified by diagnostic category (primary mood vs. primary anxiety/traumatic stress). In the basic COGENT training program framework, participants will view a series of items to be remembered, following by a secondary processing task where sentence puzzles are

solved. Participants will receive feedback about their accuracy at the conclusion of each set, and an adaptive algorithm will be used to ensure enough difficulty is maintained. The algorithm titrates advancement to the next trial based on meeting at least 85% accuracy on the prior set of trials. Our preliminary data indicate that a session frequency of 8 sessions, delivered twice weekly for 4 weeks (approximately 30 minutes per session) sufficiently improved cognitive performance. Participants assigned to COGENT will be randomized to complete dosing previously established in our work, 8 sessions over 4 weeks or a dosing of 16 sessions over 4 weeks based on literature indicating that training durations of 8 hours may be most effective. Randomization will be generated by [name] and will be securely transmitted to the study coordinator. Task-based adherence data will be collected (number of sessions, frequency). Participants assigned to waitlist will be given the option to complete COGENT after all assessments if they wish.

COVID-19 Considerations: During the COVID-19 crisis, participants may be asked to complete the consenting, screening and screening measures, and cognitive paradigms using HIPAA compliant UCSD Zoom telehealth technology to minimize in-person contact. For in-person tasks, all UCSD and Keck safety procedures will be implemented based on the current Ramp Up phase.

Clinical monitoring: We will administer a brief questionnaire at the treatment mid-point, including the GAD7, PhenX depression, and RNT-10 for purposes of identifying individuals with increased symptoms. Any individual reporting >20% increase in inventories will be referred to the PI for evaluation per the Risk Management plan below.

Table: Assessments by visit	Active groups	Waitlist group

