Screening visit MINI CSSRS MRI safety OSU-TBI RNT-10 Demographics GAD-7 Phenx Depression PhenX DSM RRS PSWQ WHODAS CTQ PANAS ACS ERQ PCL-5 AUDIT/DAST/Phenx Nicotine ISI Suicide Cognitions Treatment credibility	X	x
Midpoint clinical check GAD7 Phenx Depression RNT-10	X	
Baseline visit Cognitive assessments MRI	X	X

Cognitive training	X	
Post visit 1 (same as screening visit)	X	X
Post visit 2 (same as baseline visit)	X	X

STATISTICAL DESIGN AND POWER

Primary outcomes: Change in working memory and repetitive negative thinking. To determine whether COGENT engages the target as hypothesized (i.e., improving Ospan behavioral performance), we will analyze the effect of COGENT versus the control on the Ospan total correct score in a 2 (group: combined COGENT conditions, control) x 2 (time: pre-training, post-training) analysis of variance (ANOVA). Our hypothesis will be supported by a significant training by time interaction effect ($p < .05$; medium-large effect size based on power calculations). To investigate optimal dosing of COGENT training, effect size estimates will be compared by dose (8 vs. 16 sessions) for differences in mean change pre- to post-training. This analytic approach will be repeated for the RNT-10 Repetitive Negative Thinking and other symptom measures.

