Secondary outcome of cognitive training neural generalization effects: Images will be co-registered using AFNI's 3dvolreg program conducted with the EPI image that results in the smallest adjustment in motion parameters (x, y, z, roll, pitch, yaw). Data will be preprocessed for despiking, censoring outliers, and blurred with an applied Gaussian blur of 4.0mm and transformed into MNI coordinates. The time series of motion parameters will be used to obtain an average for these six motion parameters for each subject, and subjects will be excluded if the average in any one of these parameters exceeds 2 standard deviations from the mean of the distribution of these average motion parameters. A multivariate regressor approach detailed below will be used to relate changes in EPI intensity to differences in task characteristics. A 0-1 reference function will be convolved with a gamma-variate function to model a prototypical hemodynamic response (6-8 second delay) and to account for the temporal dynamics of the hemodynamic response (typically 12-16 seconds). The convolved time series will be normalized and used as a regressor of interest. A series of regressors of interest, polorts for detrending, and the motion regressors will be entered into the AFNI program 3dDeconvolve to determine the height of each regressor for each subject. Voxel-wise normalized relative signal change will be obtained by dividing the regressor coefficient by the sum of the zero-order regressor and the mean first-order regressor. AFNI 3dREML will be used to reduce the false positives induced by cross correlations of the time series.

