Group level analyses- the outcomes for the fMRI tasks are the difficulty regressor for the Rspan and emotional working memory tasks. The data will be entered into a mixed effects model, which offers a flexible framework to model the sources of variation and correlation that arise from grouped data (AFNI 3dLME). Once voxel-wise statistics have been calculated, we will use a threshold adjustment based on Monte-Carlo simulations in *a priori* functional regions of interest (ROIs) defined by neuroanatomical atlases of the frontoparietal circuit (NeuroSynth v5 "working memory" Topic 045) with FDR correction ($p < .05$) to guard against identifying false positive activations. The linear mixed effects model will include Group (COGENT vs. control) and Condition (interference vs. baseline) as between-subject factors and Time (pre-training, post-training) as the within-subjects factor, with subject included as a random factor.

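### Aim 1 promises an optimal-dose answer on neural as well as behavioural measures, but the fMRI model pools the two doses, so no neural dose effect is ever estimated

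*Combined protocol and SAP*

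**What the plan says.** The dose question is stated twice with a neural component. The lay summary (section 5) gives as the first objective to "determine the optimal dose of a cognitive training program designed to improve executive functioning in this population using behavioral and neural outcomes". Aim 1 (section 6) is to "Identify the cognitive effects and optimal dose of COGENT to improve executive functioning measured behaviorally (cognitive task) and neurally (fMRI"), and adds that an effect size benchmark will show whether 16 sessions bring more benefit than 8. No value is given for the benchmark.

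The analyses are in section 9:

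- **Ospan (Statistical Design and Power, primary outcomes).** The main test pools the doses against control in a 2 x 2 ANOVA. For dosing, "effect size estimates will be compared by dose (8 vs. 16 sessions) for differences in mean change pre- to post-training". No interval is mentioned.
- **Symptoms (same paragraph).** "This analytic approach will be repeated for the RNT-10 Repetitive Negative Thinking and other symptom measures". Imaging is not listed.
- **fMRI (Group level analyses).** "The linear mixed effects model will include Group (COGENT vs. control) and Condition (interference vs. baseline) as between-subject factors", with Time as the within-subject factor and subject as a random factor. There is no dose term.

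The opening of section 9 gives imaging a narrower role: "Neural activation will be used to assess generalization of training effects across multiple units of analysis".

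**The concern.** An aim that names a neural dose answer needs an analysis that can produce one. A contrast of all COGENT participants with control estimates the average effect of the two doses. It says nothing about whether 16 sessions change activation more than 8. The scans that could answer this are already planned for both dose groups, so only the model specification is missing. If nothing is specified in advance, the report will either leave out the neural dose result or contain a contrast chosen after the images have been seen. With voxel-wise data and two tasks, that leaves considerable freedom.

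The behavioural side has a smaller, related gap. The by-dose comparison for Ospan is planned, but as effect size estimates with no stated measure of uncertainty. In groups this small, a bare estimate could be read as a dose recommendation when the data are compatible with an advantage for either dose.

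**Working it through.** **Step 1: match the objective to the analyses.**

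| Measure | Dose question posed? | By-dose analysis given? |
|---|---|---|
| Ospan | Yes (Aim 1) | Yes, effect sizes, no interval |
| RNT-10 and other symptoms | Not under Aim 2 | Yes, same approach, no interval |
| fMRI, both tasks | Yes (section 5, Aim 1) | No |

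The fMRI methods before the group-level paragraph cover preprocessing and subject-level modelling, and add no group comparison. No other section gives a neural dose analysis.

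**Step 2: which fMRI contrast would answer the question.** The target is control over interference. The group-level text includes Condition (interference against baseline) as a factor, but also names the difficulty regressor as the outcome. If Condition is in the model, the relevant effect is dose x Time x Condition; a dose x Time contrast would average over interference and baseline and could miss the change of interest. If the outcome entered is already the difficulty regressor, dose x Time is the right contrast.

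**Step 3: precision of the by-dose difference for Ospan and RNT-10.** The plan states no figure to reproduce. Inputs:

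- COGENT n = 32, control n = 32 (section 9, randomization paragraph).
- 75 randomized, 65 evaluable (section 10).
- Equal split between doses: assumed, as the ratio is not stated. This gives 32/2 = 16 per dose.
- Upper range: if all 75 contributed in the same 32:32 proportions, 75/2 = 37.5 would be in COGENT, or 18 to 19 per dose.
- Unit: SD of the pre-to-post change, assumed equal in the two doses.

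Half-width of the 95% interval for 16 minus 8 = t(0.975, 2n - 2) x sqrt(2/n):

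- n = 16: 2.042 x 0.354 = 0.72
- n = 18: 2.032 x 0.333 = 0.68
- n = 19: 2.028 x 0.324 = 0.66

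At 16 per dose, an observed advantage of 0.3 SD for 16 sessions has an interval of 0.3 ± 0.72, or -0.42 to 1.02. An observed 0.5 SD gives -0.22 to 1.22. The true difference needed for an 80% chance that the interval excludes zero is 1.02 SD at 16 per dose and 0.93 to 0.96 SD at 18 to 19.

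**Step 4: dependence on the unit.** The plan does not say how effect sizes are standardized. With baseline SD and an assumed pre-post correlation of 0.7, the change SD is sqrt(2 x (1 - 0.7)) = 0.775 baseline SD, and the half-width at 16 per dose is 0.72 x 0.775 = 0.56. The interval for an observed 0.3 or 0.5 still includes zero.

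**The case against.** The best reply is that imaging was never meant to choose the dose. Section 9 assigns it to generalization of training effects, and the pooled contrast does that job. The plan promises no powered dose test, and comparing effect sizes is a reasonable choice in a small dose-finding study. Nothing in section 9 forbids intervals, so the interval point is partly about reporting.

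Much of this stands. The pooled fMRI test is suitable for its stated role and should remain the main one. The reply does not remove the conflict, because sections 5 and 6 both tie optimal dose to neural outcomes. Either the aim or the model has to change.

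A reader might also infer that the plan leaves open whether Ospan or RNT-10 decides the dose, and so risks contradictory answers. The documents do not support that. Section 6 puts dose and its benchmark under Aim 1, on executive functioning; Aim 2, on clinical effects, does not mention dose. Ospan leads, and RNT-10 is descriptive.

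**Conclusion.** The point holds. The plan promises a neural dose comparison and specifies no analysis that estimates it. This follows from the text alone and needs no assumption. It does not touch the pooled primary test or the main fMRI test, and it can be put right before dose data are examined.

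The interval point is secondary. Its size, about 0.72 change-score SD (0.66 to 0.68 at 18 to 19 per dose), rests on an equal split between doses and on the change-score SD as the unit.

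Three further inferences would go too far:

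- **Larger dose groups.** Dividing the 65 evaluable participants into three equal arms would enlarge each dose group, but section 9 gives 32 and 32.
- **The same half-widths for fMRI.** They describe a single change score, whereas the planned analysis is voxel-wise within regions of interest, with correction, for two tasks. All that can be said is that the neural dose contrast will be imprecise, and that motion exclusions ("subjects will be excluded if the average in any one of these parameters exceeds 2 standard deviations from the mean") can only reduce the numbers.
- **No dose rule at all.** A benchmark is named, and 8 sessions is the evident reference ("dosing previously established in our work, 8 sessions over 4 weeks"). Stating its value would be a useful clarification, no more.

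**What to change.** 1. **fMRI model (section 9, Group level analyses).** Give Group three levels: control, 8 sessions, 16 sessions. Keep combined COGENT against control as the main test. Add as a supportive contrast the 16-minus-8 difference in pre-to-post change in the interference effect: dose x Time x Condition, or dose x Time if the outcome entered is already the difficulty regressor. State which applies. Do this for both tasks, under the same region-of-interest and FDR correction.
2. **Alternative to 1.** Limit the dose question in sections 5 and 6 to behaviour, which fits the generalization role that section 9 gives to imaging.
3. **Behavioural and symptom dose comparison (section 9, primary outcomes).** Report the 16-minus-8 difference in mean change with its 95% interval for Ospan, as the leading dose measure, and descriptively for RNT-10. Say which SD standardizes the effect size. The interval is there to show uncertainty; it need not become a significance hurdle on top of the benchmark.
4. **Clarification.** State the benchmark value before dose data are seen.

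The cost is one more model level, a few additional corrected maps, two intervals and some lines of text, with no new participants or scans. The downside is that the intervals reveal the imprecision without reducing it, and the neural dose contrast may well be inconclusive.

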10. HUMAN SUBJECTS

The current study will recruit 95 individuals enrolled at UCSD with a diagnosis of mood, anxiety, or traumatic stress disorder from psychiatric and primary care clinics. The study will overrecruit with the goal of randomizing 75 individuals for a final evaluable sample of 65.

Inclusion criteria will include:

- 1) age 21-55
- 2) fluent in English (sufficient to understand and complete assessments in English)
- 3) diagnosis of mood, anxiety, or traumatic stress disorder
- 4) clinically elevated repetitive negative thinking

- 5) outpatient status
- 6) 6-week stability if taking SSRI medications

Exclusion criteria will include:

- 1) past year diagnosis of severe alcohol or moderate or greater substance use disorder
- 2) lifetime history of psychotic or bipolar I disorder
- 3) acute suicidality necessitating immediate clinical intervention
- 4) neurodegenerative or neurodevelopmental disorders
- 5) history of moderate or severe traumatic brain injury or other known neurological condition
- 6) sensory deficits that would preclude completing tasks
- 7) conditions unsafe for completing MRI scanning (e.g., metal in body)
- 8) currently receiving psychosocial treatment
- 9) currently receiving psychiatric pharmacotherapy, except SSRIs

There are no inclusion/exclusion criteria pertaining to gender, ethnic background, or health status aside from MRI safety requirements stated above.

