In terms of other fMRI related issues, to minimize the risk of fear of closed spaces while in the MR scanner, patients will be extensively interviewed and informed about the nature of the task. We have previously used pictures of the MR scanner to familiarize subjects with the scanner environment. During scanning the investigator can hear the subject at all times and if, at any point in during the scanning, the subject expresses increasing discomfort, the operator will immediately intervene and terminate the scanning procedure. There is the possibility of an abnormal finding on the fMRI scan. However, the fMRI scans are not being done for clinical purposes, and the fMRI scan procedure is not sufficient for the clinical diagnosis of a possible brain disorder. The purpose of this scan is not to diagnose abnormalities, but on rare occasions a finding is observed that might be clinically important. Should there be cause for concern, we will forward to neuroradiology. Participants will be told about the potential discomforts associated with lying in the scanner for approximately 60 minutes. During scanning, subjects' heads and necks will be supported for maximum comfort, and earplugs and headphones will be required in the MRI scanner to protect from the noise produced by the scanner. The individuals will be given an alarm button, which they will be able to press if there is any discomfort or distress. Pregnancy testing with immediate results will ensure that no pregnant individual receives an MRI. Pregnancy testing results will be discussed with participants, and counseling will be provided should the participant indicate significant distress. In order to address any concerns regarding coercion, subjects will be informed that they are free to choose not to participate and may withdraw at any time (this is included in the consent form).

Participants may terminate the study or any parts of the study at any time. During scanning the investigator can hear the subject at all times and if, at any point in during the scanning, the subject expresses increasing discomfort, the operator will immediately intervene and terminate the scanning procedure.

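### The aims describe COGENT by completion and waitlist by assignment; with a paired-visit ANOVA and 65 evaluable of 75 randomised, a completer analysis of Ospan and RNT-10 is left open

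*Combined protocol and SAP*

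**What the plan says.** Section 6 states Aim 1 as the hypothesis that "individuals completing COGENT will show improved executive functioning on behavioral and neural measures relative to those assigned to the waitlist condition". Aim 2 repeats the completion wording for symptoms: "We hypothesize that individuals completing COGENT will show a reduction in repetitive negative thinking". The dose question in Aim 1 is likewise put in terms of finishing 16 rather than 8 sessions.

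Section 9, Statistical Design and Power, says "we will analyze the effect of COGENT versus the control on the Ospan total correct score". The model named for this contrast is the following: "2 (group: combined COGENT conditions, control) x 2 (time: pre-training, post-training) analysis of variance (ANOVA"). The same approach is carried over to the RNT-10 and other symptom measures. Dose is judged by comparing effect sizes for mean change, with no test named.

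Section 10 gives the "goal of randomizing 75 individuals for a final evaluable sample of 65" and does not define evaluable. Section 9 places the primary assessments "at two time points: baseline pre-training and immediately post-training". Section 15 adds: "Participants may terminate the study or any parts of the study at any time".

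The document contains no statement that participants are analysed as randomised, no analysis-set definition, no missing-data method and no sensitivity analysis. Session counts are collected (Section 9), and retention by condition goes to the safety monitor (Section 15). Neither is given a role in the analysis.

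**The concern.** Completing training is a post-randomisation event; being assigned to waitlist is not. If the COGENT group were reduced to completers while the control group stayed whole, the comparison would no longer be the randomised one. A two-visit ANOVA could have a similar effect without any explicit exclusion, because people without a post score disappear from it.

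The burdens differ by design. COGENT participants do 8 or 16 sessions of adaptive training in 4 weeks. Controls wait and may take up COGENT once all assessments are done. It is plausible that people who leave training are those doing poorly, and that reasons for leaving differ by arm. Selective loss could then look like benefit on both primary outcomes, and selective loss from the 16-session group could look like added value of the higher dose. Because the plan does not fix the population, the choice could also be made after the results are known.

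**Working it through.** **1. What the text commits to.** Section 6 uses completion for COGENT and assignment for waitlist. Section 9 compares combined COGENT with control and states no completion rule. Section 10 gives a target of 65 without saying who the other 10 are. Together these neither require nor exclude a completer analysis.

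**2. The plan's own loss.** (75 − 65)/75 = 13.3%. Section 9 gives 32 + 32 = 64, which would make it 11/75 = 14.7%.

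**3. A yardstick.** The plan gives no numeric effect size, SD or power. Assuming two-sided 5% and 80% power with 32 per group, the detectable difference is (1.960 + 0.842) × √(2/32) = 0.70 SD of change, which fits the plan's description of a medium-large effect.

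**4. Simulation with no true effect.** 75 randomised as 38 COGENT and 37 control (1:1 assumed), 10 lost, 20,000 trials per scenario. The test is a t-test on change among those retained, which is equivalent to the 2×2 interaction test. Those lost rank worst on a latent propensity that has correlation r with poor change. The splits and r values are assumptions. Entries are bias in SD of change, with the two-sided false-positive rate in brackets.

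Same loss mechanism in both arms:

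| Losses COGENT/control | r = 0.3 | r = 0.5 |
|---|---|---|
| 5/5 | about 0 (5%) | about 0 (6%) |
| 7/3 | 0.05 (6%) | 0.08 (7%) |
| 8/2 | 0.07 (6%) | 0.12 (9%) |
| 10/0 | 0.13 (8%) | 0.22 (14%) |

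COGENT loss related to poor change, control loss random:

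| Losses COGENT/control | r = 0.2 | r = 0.4 | r = 0.6 |
|---|---|---|---|
| 5/5 | 0.05 (5%) | 0.10 (7%) | 0.14 (9%) |
| 8/2 | 0.07 (6%) | 0.14 (9%) | 0.22 (15%) |
| 10/0 | 0.08 (6%) | 0.17 (11%) | 0.26 (19%) |

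Check: bias is proportional to r. For 10/0 at r = 1 it is 0.433, so 0.433 × 0.4 = 0.17 and 0.433 × 0.6 = 0.26, as tabulated. When loss is unrelated to change (r = 0), bias is about 0 and the error rate about 5% for every split.

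Against the yardstick, the 10/0 split at r = 0.3 to 0.5 gives 0.131/0.70 = 19% to 0.216/0.70 = 31% of the detectable difference.

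**5. Dose.** With 19 per dose (even split assumed), 4 lost selectively from 16 sessions and 1 at random from 8, and no true difference, 16 sessions looks better by 0.07, 0.14 and 0.21 SD at r = 0.2, 0.4 and 0.6.

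**6. What a mixed model alone would do.** Approximating a common-baseline model by ANCOVA on those retained, with pre-post correlation 0.6 assumed, the bias at r = 0.4 falls from about 0.14 to 0.11 SD for 8/2 and from 0.17 to 0.14 SD for 10/0. Most of it remains, because loss here depends on change that is not observed.

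**The case against.** A reader might infer that the plan analyses only completers, or only the 65. The documents do not say so. The completion wording appears only in the aims and can be read as loose phrasing for receiving training. The opening of Section 6 and the hypotheses in Section 9 compare COGENT with control without it. The 65 is a recruitment target. The 10 others could be missed visits or unusable scans, since Section 9 excludes subjects for head motion, which has no stated link to Ospan or RNT-10.

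Nor does stopping training mean missing the post visits. The assessment table in Section 9 schedules both post visits for active and waitlist groups without requiring finished sessions. Training lasts 4 weeks at either dose and controls are assessed at matching times, so the post date is largely implied. Section 20 pays for assessment visits separately from training weeks. Someone who stops early could attend and be kept in the ANOVA.

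The larger biases need unequal loss or different reasons for loss, and the documents quantify neither. Waitlist participants may also leave because they are not improving. Finally, the fMRI outcome already uses a mixed effects model, so the ANOVA argument does not reach the neural half of Aim 1.

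All of this stands, and it narrows the point. What it does not supply is a rule. No section says that early stoppers are invited back, that they are kept in their assigned group, or what happens to a missing post score.

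**Conclusion.** The point holds as an under-specification that leaves a completer analysis of Ospan and the symptom measures open. It does not hold as a claim that such an analysis is planned. The expected loss of 13.3% is the plan's own figure.

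With unequal loss related to poor change, the spurious benefit runs from about 0.05 SD (7/3, r = 0.3) to 0.26 SD (10/0, r = 0.6), with false-positive rates of about 6 to 19%. With balanced loss and the same mechanism in both arms it is about zero. A reader might conclude that the design favours COGENT, or 16 sessions over 8. That direction is plausible from the difference in burden, but the documents give no drop-out rate by arm and no outcome for those lost, so it is not established. The dose figures rest on assumed losses in the same way.

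**What to change.** 1. Reword Aims 1 and 2 and the primary-outcome paragraph of Section 9 so that the primary comparison is all randomised participants by assigned arm, and by assigned dose for 8 versus 16, whatever number of sessions they completed.
2. State in Section 9 that Post Visits 1 and 2 fall at the end of the 4-week period in every arm, and that people who stop training are still invited unless they withdraw from assessment. This does the most to reduce the bias, because it reduces the missing data.
3. Replace the ANOVA with a likelihood-based mixed model on all available baseline and post scores, with a common baseline mean. Add a sensitivity analysis for non-random loss, for example worsening the assumed post scores of those lost from COGENT until the conclusion changes. The model alone does not remove that bias.
4. Define evaluable in Section 10. Use the session counts for any completer analysis, labelled as secondary and non-randomised.

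The cost is wording and a different model, with no extra participants or procedures. The downside is that the estimated effect may be somewhat smaller. The changes should be settled before outcome data are seen.
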